**TITLE:**  
**EARLY THERAPEUTIC MONITORING OF RESPONSE TO THERAPY**  
**WITH SERIAL ULTRASOUND IN METASTATIC RENAL CELL CARCINOMA**

Document History	Notes
Version 1.0 Date: 19 Aug, 2020	Initial Approval
Version 2.0 Date: 16 Jan, 2021	
Revisions include:
 
 
• updated list of co-investigators
 
• relaxation of allowable time window for 6-week US exam (+/- 15 days instead of +/- 8 days)
 
• option added to obtain consent from Legally Authorized Representatives (LARs)
 
• option added to obtain written consent from English-speaking participants/LARs online via RedCAP
 

Version 3.0 Date: 28 Apr, 2021	
Revisions include:
 
 
• updated list of co-investigators
 
• clarification of inclusion criteria (section 3.1)
 
• inclusion of other ultrasound transducers
 

Version 4.0 Date: 28 Jun, 2021	
Revisions include:
 
 
• updated list of co-investigators
 
• correction of protocol title
 

Version 5.0 Date: 12 Jul, 2022	
Revisions include:
 
 
• updated list of co-investigators
 
• additional exploratory study arm 2 defined: patients receiving any non-immune checkpoint inhibitor treatment (e.g., TKI monotherapy, combination of TKI with other kinase inhibitor, localized tumor therapy such as radiation, chemo- or radioembolization)
 
• participant population expanded to patients referred to Stanford from outside institutions for participation in this study
 
• clarification added to study calendar on definition of start of treatment
 
• minimum time period of 10 days between 'week-3' and 'week-6' ultrasound exams defined in study calendar
 
• use of RedCAP for electronic signatures on consent forms replaced by Adobe Sign
 
• correction of typos and unclear wording
 

Version 5.0 Date: 27 Jul, 2022 (revisions after start of SRC review)	
Revisions include:
 
 
• triple eligibility check replaced by single eligibility check by treating provider (incl. APPs)
 

Version 6.0 Date: 4 Oct, 2022	
Revisions include:
 
 
• updated list of co-investigators
 
• option added for non-licensed, qualified staff to perform research ultrasound exams
 

Version 7.0 Date: 21 Nov, 2022	
Revisions include:
 
 
• AE evaluation schedule revised, now tied to study procedures instead of SOC visits
 

Version 8.0 Date: 30 Jan, 2023	
Revisions include:
 
 
• management of ultrasound imaging data and associated PHI clarified (section 8.2)
 
• Appendix A: lines for provider initials and date for subjective exclusion criterion added
 

Early Therapeutic Monitoring of Response to Therapy with Serial Ultrasound in Metastatic Renal Cell Carcinoma

Version 9.0	Date: 1 May, 2023	
Revisions include:
 

• updated list of co-investigators

• criteria for removal from study clarified (section 5.1)

• data management procedures upon study closure clarified (section 8.2)

-------------	-------------------	--

Protocol Directors

[figure not shown]

## PROTOCOL SYNOPSIS

TITLE	Early therapeutic monitoring of response to therapy with serial ultrasound in metastatic RCC
STUDY PHASE	Pilot
INDICATION	Metastatic Renal Cell Carcinoma (mRCC)
INVESTIGATIONAL PRODUCT OR PROCEDURE	Study of power Doppler ultrasound for early detection of therapeutic response after initiating therapy with: arm 1: tyrosine kinase (TKI) inhibitor plus immune checkpoint inhibitor (ICI) arm 2: non-ICI therapy (e.g., TKI monotherapy, combination of TKI with other kinase inhibitor, localized tumor therapy such as radiation, chemo- or radioembolization)
PRIMARY OBJECTIVE(S)	To assess whether changes in quantitative tumor perfusion parameters after 3 weeks of treatment, as measured by LEAD ultrasound, can predict initial objective response, defined by current standard-of-care, to therapy at 12 weeks after start of treatment
SECONDARY OBJECTIVE(S)	To evaluate if there is an optimal ultrasound imaging modality (power Doppler or LEAD ultrasound) or optimal time point to predict initial objective response, to assess the correlation of tumor perfusion parameters with change in overall tumor burden, change in diameter on a per-lesion basis and with 12-month progression-free survival (PFS).
STUDY PROCEDURE SUMMARY	power Doppler and LEAD ultrasound of subjects taking targeted therapy medication, measured at treatment 'baseline', 3-4 weeks, and 6-8 weeks after initiating treatment
SAMPLE SIZE	arm 1: 20 subjects arm 2: up to 10 subjects
STATISTICAL CONSIDERATIONS	We will evaluate the predictive ability of each model using area under the curve (AUC). For this pilot study, assuming that 59% of patients in arm 1 have an objective response to treatment, a predictive model with a true AUC of 0.7 will have a margin of error of 0.14 so that the estimated AUC can range from 0.56 to 0.84.

## SCHEMA

## LIST OF ABBREVIATIONS AND DEFINITION OF TERMS

AE	Adverse Event
AUC	Area Under the Curve
CART	Classification And Regression Tree
CEUS	Contrast-Enhanced Ultrasound
CR	Complete Response
CRF	Case Report Form
CT	Computed Tomography
CTCAE	Common Terminology Criteria for Adverse Events
CTLA-4	Cytotoxic T-Lymphocyte-Associated Protein 4
DSMC	Data and Safety Monitoring Committee
FDA	United States Food and Drug Administration
GCP	Good Clinical Practice
ICI	Immune Checkpoint Inhibitor
IDE	Investigational Device Exemption
IRB	Institutional Review Board
Lasso	Least absolute shrinkage and selection operator
LEAD	Long Ensemble Angular-coherence Doppler
mRCC	Metastatic Renal Cell Carcinoma
OS	Overall Survival
PD	Progressive Disease
PD-1	Programmed Cell Death Protein-1
PD-L1	Programmed Death Ligand-1
PET	Positron Emission Tomography
PFS	Progression-Free Survival
PR	Partial Response
RECIST	Response Evaluation Criteria In Solid Tumors
RCC	Renal Cell Carcinoma
SAE	Serious Adverse Event
SD	Stable Disease
SOP	Standard Operating Procedure
SRC	Scientific Review Committee
TKI	Tyrosine Kinase Inhibitor
VEGFR2	Vascular Endothelial Growth Factor Receptor 2

## 1. OBJECTIVES

### 1.1 Primary Objective

Our primary objective is to assess whether in arm 1, changes in quantitative tumor perfusion parameters 3 weeks after start of treatment of metastatic renal cell carcinoma (mRCC) patients with tyrosine kinase inhibitor (TKI) plus immune checkpoint inhibitor (ICI), as measured by LEAD ultrasound, can predict initial objective response to therapy at 12 weeks after start of treatment defined by current standard-of-care Response Evaluation Criteria In Solid Tumors (RECIST v1.1).

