## **9. MEASUREMENTS**

### **9.1 Primary Outcome Measures**

The primary endpoint is initial objective response per RECIST v1.1 assessed 8-16 weeks after start of treatment, using standard-of-care imaging. expressed as a number and proportion without dispersion.

Initial objective response (yes/no): defined as having either Complete Response (CR) or Partial Response (PR) per RECIST v1.1 at first on-treatment response evaluation 8-16 weeks after initiating treatment.

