### 9.1.1 Measurement Methods

Tumor diameter measurements: Where possible, the same lesions that were selected for repeat LEAD ultrasound exams are used as target lesions for response evaluation per RECIST. Different lesions may be selected at the discretion of the radiologist designated to review response evaluation.

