#### Selection of lesions for LEAD ultrasound exams:

Before the first ultrasound exam, the treating medical oncologist, a Protocol Director, or a designated radiologist selects up to 5 lesions per patient (target lesions per RECIST v1.1). At the treatment 'baseline' LEAD ultrasound exam (up to 28 days prior to start of treatment), perfusion of these 5 lesions is measured. Additional lesions may be assessed at the discretion of the investigators, so that in the end up to 5 lesions are selected for repeat ultrasound exams that in the opinion of the investigators lend themselves to reproducible tumor perfusion measurements. LEAD ultrasound tumor perfusion measurements of the up to 5 lesions that were selected for ultrasound studies at the treatment 'baseline' exam are performed again 3 weeks (+/- 8 days) after start of treatment.

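### Section 9.1.1 lets ultrasound suitability steer the choice of RECIST target lesions, so the AUC can overstate prediction of overall response

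*Protocol*

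**What the plan says.** Protocol section 1.1 names the response to be predicted as the one "defined by current standard-of-care Response Evaluation Criteria In Solid Tumors (RECIST v1.1").

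The endpoint in Protocol section 9.1 is patient-level and binary: "defined as having either Complete Response (CR) or Partial Response (PR) per RECIST v1.1 at first on-treatment response evaluation", read on standard-of-care imaging at 8-16 weeks.

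Three further places decide which lesions count:

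- **Initial choice (10.3.2, selection of lesions).** Before the first ultrasound exam an oncologist, a Protocol Director or a radiologist "selects up to 5 lesions per patient (target lesions per RECIST v1.1").
- **Revision at the baseline exam (same paragraph).** Further lesions may be assessed, and the final set of up to 5 consists of those "that in the opinion of the investigators lend themselves to reproducible tumor perfusion measurements".
- **Link to the reference standard (9.1.1).** "Where possible, the same lesions that were selected for repeat LEAD ultrasound exams are used as target lesions for response evaluation per RECIST". An exception follows: "Different lesions may be selected at the discretion of the radiologist designated to review response evaluation". No criterion is given for using it.

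The predictor, defined under quantification of tumor perfusion parameters in 10.3.2, is the average relative perfusion change over that same final set. Section 10.7 makes an AUC of at least 0.7 the condition for a follow-up study.

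**The concern.** A reference standard should be set without reference to the test under evaluation. Here the baseline ultrasound exam settles which lesions are re-imaged, and by default those lesions become the RECIST targets.

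The two sets can differ. Section 3.1 requires only one ultrasound-accessible lesion larger than 1 cm, while footnote b of the study calendar prefers a response scan covering chest, abdomen and pelvis. A patient may therefore have measurable disease that ultrasound does not reach.

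Lesions in one patient need not change together. A predictor taken from certain lesions will usually track shrinkage of those lesions at least as well as shrinkage of the whole disease. If the target sum rests mainly on the imaged lesions, the AUC partly answers a narrower question than section 1.1 asks. That AUC feeds the go criterion, and the programme described in 10.7 leads to a trial of early therapy switch, which is a decision about the patient and not about selected lesions.

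**Working it through.** **Inputs from the plan.** 20 patients, 59% responders and an AUC of 0.7 regarded as promising (10.5); up to 5 lesions (10.3.2). The plan gives no number of measurable lesions per patient, no share reachable by ultrasound and no within-patient correlation of lesion response. These are assumed below.

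**The plan's own figure.** None concerns lesion overlap. The nearest is the AUC margin of 0.14 in 10.5, used here only for scale. Hanley-McNeil with A = 0.7, n1 = 0.59 × 20 = 11.8, n2 = 8.2:

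- Q1 = 0.7/1.3 = 0.5385; Q2 = 2 × 0.49/1.7 = 0.5765
- Variance = [0.21 + 10.8 × (0.5385 − 0.49) + 7.2 × (0.5765 − 0.49)]/(11.8 × 8.2) = 0.0140
- SE = 0.118; 95% half-width = 1.96 × 0.118 = 0.23

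The stated 0.14 is therefore not reproduced as a 95% margin. That is a separate matter and does not bear on this point.

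**Why sharing lesions matters.** Let each lesion's response have variance 1 and within-patient correlation ρ. The mean over k lesions has variance V(k) = ρ + (1 − ρ)/k. If m lesions are imaged out of M, the predictor's correlation with the all-lesion mean equals its correlation with the imaged-lesion mean times √[V(M)/V(m)].

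- ρ = 0.3, m = 1, M = 3: √(0.5333/1) = 0.730. An assumed correlation of 0.5 falls to 0.365.
- ρ = 0.9, m = 1, M = 3: √(0.9333/1) = 0.966. The correlation falls only to 0.483.
- ρ = 0.9, m = 3, M = 5: √(0.92/0.9333) = 0.993. There is almost no loss.
- If all M measurable lesions are targets, the target set and the all-lesion set coincide and the overstatement is zero.

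**Model 1.** 200,000 simulated patients per setting, 59% responders, lesion-level correlation of perfusion change with shrinkage 0.5. Each cell shows the AUC against response in the imaged lesions, the AUC against response in all lesions, and the difference:

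| ρ | 1 imaged + 2 others | 2 imaged + 3 others | 3 imaged + 2 others |
|---|---|---|---|
| 0.3 | 0.732, 0.665 (0.067) | 0.756, 0.710 (0.046) | 0.776, 0.748 (0.028) |
| 0.5 | 0.732, 0.690 (0.042) | 0.770, 0.742 (0.028) | 0.796, 0.780 (0.016) |
| 0.7 | 0.734, 0.708 (0.026) | 0.780, 0.764 (0.016) | 0.813, 0.805 (0.008) |
| 0.9 | 0.730, 0.723 (0.007) | 0.793, 0.787 (0.006) | 0.831, 0.827 (0.004) |

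In two of the twelve settings (one lesion imaged of three, ρ = 0.3 or 0.5) the AUC moves from above 0.7 to below it.

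**Model 2.** 100,000 patients per setting; 3-5 measurable lesions of which 1-3 are imaged; SD of log diameter change 0.35; ρ from 0.3 to 0.7; equal baseline diameters; response a fall of at least 30% in the sum. The predictor is calibrated to AUC 0.70 on the imaged lesions. Against all measurable lesions the AUC is 0.63 to 0.70, so the loss runs from 0.70 − 0.631 = 0.069 to 0.70 − 0.696 = 0.004. Responder status differs between the two sets in 6-26% of patients: 0.06 × 20 = 1.2 to 0.26 × 20 = 5.2, or about 1 to 5 of 20.

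Both models score the reference on the imaged lesions alone. Both ignore non-target and new lesions, and neither reproduces the cross-validated Lasso with clinical covariates.

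**The case against.** The case for leaving the text alone has real weight.

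- **Selection begins from RECIST status.** The first set consists of RECIST target lesions; ultrasound measurability enters only at the second step. This stands, and it limits how far the sets can drift apart. Even so, 9.1.1 refers to the lesions kept for repeat exams, which is the revised set.
- **Exclusion is not stated.** A reader might infer that disease out of ultrasound reach is left out of the response assessment. The documents do not say so. Section 9.1.1 does not confine the targets to the ultrasound lesions, the endpoint remains CR or PR per RECIST v1.1, and nothing removes non-target or new lesions from that reading. The simulated losses apply only if the targets are the ultrasound lesions alone.
- **Circularity.** A reader might also call the design circular. It is not: lesions are fixed before treatment, the predictor is Doppler power at week 3, and the reference is diameter at about week 12 on another modality. What is at issue is how far the AUC carries over to overall response.
- **Safeguards.** The radiologist may depart from the default, the eCRF identifies both sets of lesions (8.2), and perfusion change is also correlated with overall tumor burden (10.4.2). These help. However, departure has no criterion, and 9.2.1 takes diameter measurements for the secondary endpoints the same way as for the primary one.
- **Small consequence.** This is a pilot, and 0.07 is below even the stated 0.14 margin. That is true of the shift against sampling error. But it is a bias, and it would persist in a larger follow-up study that copied the same target rule.

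**Conclusion.** The point holds in a limited form. As written, the ultrasound exam can steer which lesions define response, while section 1.1 sets the goal as standard-of-care RECIST response. The AUC can therefore overstate prediction of overall response; it cannot be said that it does.

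The size, about 0.00 to 0.07, rests wholly on assumed lesion counts and correlations and on the targets being the ultrasound lesions alone. It is largest when few lesions are imaged and lesions respond differently. It is near zero when they respond alike or when the other measurable lesions are also targets. The stronger claim, that the reported AUC is inflated by a known amount, has no support in the documents. This is a cheap improvement to the endpoint definition and not a flaw that invalidates the pilot.

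**What to change.** In section 9.1.1, replace the same-lesion default for the primary endpoint. State that the designated radiologist selects the target lesions from the baseline standard-of-care scan by RECIST v1.1 rules, without regard to suitability for ultrasound. Add that baseline and week-12 diameters are also recorded for any ultrasound lesion that is not a target, and that these are used only for the per-lesion endpoint (9.2, item 2), where same-lesion comparison belongs.

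The cost is a wording change and up to 5 extra diameters per scan, by the same radiologist on scans already obtained. The AUC may come out slightly lower, but it would then refer to the response named in the primary objective and could fairly be compared with 0.7.

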### 1.2 Secondary Objectives

Our secondary objectives are to evaluate in arm 1, if there is an optimal ultrasound imaging modality (power Doppler or LEAD ultrasound), or optimal time point to predict initial objective response. We will assess how well 1) changes in tumor perfusion parameters 6 weeks after start of treatment by imaging modality or 2) tumor perfusion parameters at a single time point (treatment 'baseline', 3 weeks, or 6 weeks after start of treatment), predict initial objective response (at 12 weeks) per RECIST v1.1.

Additional exploratory objectives in both arms are to assess the correlation of tumor perfusion parameters with change in overall tumor burden (defined as sum of the longest diameters of all measurable lesions defined by RECIST v1.1) 12 weeks after start of treatment, with change in diameter on a per-lesion basis (correlation between perfusion parameters of a single lesion with change in diameter of that lesion), and with 12-month progression-free survival (PFS).

## 2. BACKGROUND

### 2.1 Study Disease

Renal cancer is the 8th most common cancer in the U.S. and patients with metastatic RCC (mRCC) have a 5-year overall survival (OS) rate of 12%. There are 17 FDA-approved drugs for mRCC, which include TKIs of vascular endothelial growth factor receptor 2 (VEGFR2, a key mediator of angiogenesis), and antibodies that target immune checkpoint proteins such as programmed cell death protein-1 (PD-1), programmed death ligand-1 (PD-L1), or cytotoxic T-lymphocyte-associated protein 4 (CTLA-4).

In April 2019, the FDA approved the combinations of a TKI (axitinib) with an ICI (pembrolizumab or avelumab) for first-line treatment of mRCC and additional TKI plus ICI combination therapies (cabozantinib plus nivolumab, lenvatinib plus pembrolizumab) have been approved more recently. TKI plus ICI has become the new standard-of-care first-line treatment that improves OS for patients with mRCC.

## 2.2 Imaging Procedure

Power Doppler ultrasound is an ideal non-invasive modality for serial measurements because it can be performed at bedside during routine oncology visits. However, due to the relatively large depths at which some organs such as the kidneys are located and the low frequencies utilized to image deep structures, the ability to detect the smaller vasculature of tumors and the potential changes in tumor vasculature becomes increasingly difficult. Hence, in addition to the commercially available power Doppler imaging mode, we will incorporate advanced power Doppler imaging techniques that improve the sensitivity to slower flow and smaller vessels in our study. Specifically, this advanced power Doppler mode utilizes long Doppler ensembles combined with short-lag angular coherence beamforming to achieve high sensitivity to slow flow and small vessels (Long Ensemble Angular-coherence Doppler [LEAD] ultrasound). The long Doppler ensemble increases the sensitivity to flow by utilizing high frame rates (~300 Hz) to boost the signal-to-noise ratio of the blood signal. Moreover, angular coherence beamforming is utilized in LEAD ultrasound studies to suppress motion/flash artifact over the long ensemble while also suppressing incoherent noise due to reverberation and thermal noise.

For the ultrasound exams at treatment ‘baseline’ and 3 and 6 weeks after initiating treatment in this pilot study, lesions are imaged with B-mode and power Doppler ultrasound using a portable Siemens Acuson S3000 ultrasound scanner and a 6C1 or similar transducer (FDA-approved for clinical ultrasound exams but used only for research exams for this study). Measurements are performed in the long axis and short axis planes, if possible by tumor localization. For LEAD ultrasound exams, the same views are obtained using a Verasonics Vantage 256 scanner with a C5-2v or similar transducer (research ultrasound scanner).

## 2.3 Clinicaltrials.gov

The Verasonics system operates under an abbreviated Investigational Device Exemption (IDE) approved by the Stanford IRB. The device has non-significant risk. The study is registered at [clinicaltrials.gov](https://clinicaltrials.gov) under registration number NCT04508725.

## 2.4 Rationale

Unfortunately, not all mRCC patients respond to first-line treatment, yet all patients endure the side effects of treatment (fatigue, nausea, diarrhea, and/or liver inflammation) while awaiting standard-of-care imaging (typically computed tomography, CT) to assess response after approximately 12 weeks of therapy. Evaluation of efficacy currently requires this time period because molecular and cellular changes induced by therapy require about 12 weeks to result in definitive changes in tumor diameters on CT scans. Patients may respond to subsequent lines of therapy; yet approximately 40% of patients never receive second-line therapy despite 13 additional drugs available. Thus, rapid detection of response or resistance to RCC therapy is required to minimize use

of ineffective drugs and to allow patients to cycle through drugs to arrive at effective therapy.

Increased angiogenesis and immune system evasion are intrinsic to RCC. Clear cell RCC occurs when the von-Hippel Lindau tumor suppressor is lost, resulting in upregulation of angiogenesis and suppression of immune signaling. In RCC, blood vessels increase in number but have abnormal porosity. The abnormal porosity prevents T cells from exiting blood vessels to infiltrate and attack tumors. Immune checkpoint inhibition normalizes blood vessel porosity, allowing T cell egress. Hence changes in tumor vascularity may be especially important in RCC patients receiving TKI therapy (alone or in combination with other drugs).

We have previously found that imaging-based biomarkers (e.g., perfusion CT, '4D-CT' scans, or novel positron emission tomography [PET] tracers such as F18-FPPRGD2 that binds blood vessels) may have the capability of detecting early response to anti-angiogenic therapy in mRCC. However, due to renal dysfunction and often only a solitary remaining kidney after resection of the initial kidney primary lesion, patients are not always eligible for perfusion CT, which requires potentially nephrotoxic iodinated contrast. A limitation of PET imaging is that nuclear imaging does not provide measurements of blood flow. Hence, there is an important clinical need for complimentary, non-nephrotoxic imaging that can be serially repeated without exposure to ionizing radiation, to predict response and resistance to TKI plus ICI and other mRCC therapies.

[figure not shown]
In addition, not all patients can tolerate TKI plus ICI combination therapy, so we have added an exploratory arm 2 to investigate the ability of Doppler ultrasound to detect changes in tumor perfusion in patients who are planned to receive non-ICI therapies. These include, but are not limited to: TKI monotherapy, combination of TKI with another kinase inhibitor (e.g., mTOR inhibitor), localized tumor therapy such as radiation, radioembolization, chemoembolization. (Patients receiving ICI/ICI combination therapy or ICI monotherapy are enrolled in the parallel ultrasound study 'Serial Ultrasound to Detect Early Response to Immunotherapy in Advanced Renal Cell Carcinoma' (RENAL0045). The choice of treatment is made by the treating medical oncologist based on clinical considerations per standard-of-care (e.g., comorbidities and performance status, need for immediate control over tumor growth versus long-lasting tumor control, response to previous treatments, tolerance of previous treatments). Patients are assigned to a study arm based on the treatment plan at the time of enrollment.

Contrast-enhanced ultrasound (CEUS) has been used for the identification of renal focal lesions and has shown some promise in preliminary studies to monitor changes with therapy. However, CEUS has not widely been explored as a methodology to monitor anti-angiogenesis or combination therapy. Furthermore, the use of CEUS to monitor therapeutic response may be unnecessary, as recent advances in power Doppler imaging have yielded non-contrast, high-sensitivity perfusion imaging by using novel filter and ultrasound beamforming design

. Such methods have also been applied to monitor cancer therapy response in the liver. Doppler ultrasound is an ideal modality for serial measurements because it can be performed at bedside during routine oncology visits, without requiring placement of an intravenous catheter for administration of contrast. In this pilot study, we use conventional power Doppler and LEAD ultrasound imaging to non-invasively assess changes in tumor perfusion parameters performed in real time, with the ultimate goal to accelerate detection of response to combined TKI plus ICI therapy.

